### **9.3.5. Noninvasive Scores and NAFLD Liver Fibrosis Scores**

Noninvasive scores of liver fibrosis including FIB-4, APRI, and NFS will be summarized with descriptive statistics at Baseline and each DB post-Baseline visit. In addition, change and percentage change will be summarized and analyzed using the Wilcoxon Rank Sum Test to compare treatment groups. The median differences and 95% CI of the median differences between treatment groups will be constructed using Hodges-Lehmann estimate.

In addition, BARD score shift changes from Baseline to each DB post-Baseline visit will be summarized by treatment group.

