### **3.3.3. Markers for Hepatic Apoptosis and Fibrosis**

For the laboratory parameters cytokeratin-18 neoepitope M30 (CK-18-M30) and cytokeratin-18 neoepitope M65 (CK-18-M65):

- Observed values, change from Baseline, and percentage change from Baseline at each DB post-Baseline visit

For noninvasive scores of liver fibrosis NFS, FIB-4, and APRI:

- Observed values, change from Baseline, and percentage change from Baseline at each DB post-Baseline visit

For noninvasive score of liver fibrosis BARD:

- Shift from Baseline to each DB post-Baseline visit

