### **6.2.8. Multiple Comparisons/Multiplicity**

As this is a descriptive study, no formal adjustments for multiple comparisons are being made. Therefore, CIs and p-values will be interpreted as purely descriptive.

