$$\text{percentage change from Baseline} = 100 \times ([\text{post-Baseline value} - \text{Baseline value}] / \text{Baseline value})$$

- **Geometric Mean:** In order to calculate a geometric mean and corresponding 95% CI, the following steps are used:

- Transform the data by taking natural logarithms ( $\log_e$ )
- Calculate the mean and 95% CI of the  $\log_e$ -transformed data
- Exponentiate the mean and the lower and upper CIs back to the original scale in order to obtain the geometric mean and corresponding 95% CI.

The geometric coefficient of variation (geometric CV%) is calculated as  $100 \times \sqrt{e^{\text{SD}^2} - 1}$  where SD is the SD of the  $\log_e$ -transformed data.

- **Coefficient of Variation** - The coefficient of variation (CV%) will be calculated as the ratio of the standard deviation to the arithmetic mean using the following formula:

$$\text{Coefficient of variation} = \frac{\text{standard deviation}}{\text{arithmetic mean}}$$

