#### 6.3.7. Fibrosis Scores Calculations

Fibrosis scores (ie, NFS and APRI) will be calculated at the time of data analysis using data collected via the Medical History eCRF and the central laboratory data. The calculations are as follows:

**NFS** =  $-1.675 + 0.037 \times \text{age (years)} + 0.094 \times \text{BMI (kg/m}^2\text{)} + 1.13 \times \text{impaired fasting glucose(fasting glucose} \geq 110 \text{ mg/dL) / diabetes (yes = 1, no = 0)} + 0.99 \times \text{AST/ALT ratio} - 0.013 \times \text{platelets (}\times 10^9/\text{L)} - 0.66 \times \text{albumin (g/dL)}$

**APRI** =  $((\text{AST(IU/L)}/\text{AST upper limit of normal}) / \text{platelets (}\times 10^9/\text{L)}) \times 100$

**FIB-4** =  $(\text{Age (years)} \times \text{AST(IU/L)}) / (\text{Platelets}(\times 10^9/\text{L}) \times \text{sqrt(ALT(IU/L))})$

**BARD** score is calculated by designating 0 to 2 points to the following parameters:  $\text{BMI} \geq 28 \text{ kg/m}^2 = 1 \text{ point}$ ,  $\text{BMI} < 28 \text{ kg/m}^2 = 0 \text{ point}$ ;  $\text{AST/ALT ratio} \geq 0.8 = 2 \text{ points}$ ,  $\text{AST/ALT ratio} < 0.8 = 0 \text{ point}$ ; freshly recognized or preexisting diabetes mellitus type 2 = 1 point. A total of 2 to 4 points indicates significant fibrosis.

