## **12. CHANGES TO PROTOCOL-SPECIFIED ANALYSES AND ENDPOINTS**

There has been one change between the protocol-defined statistical analyses and those presented in this statistical analysis plan. The bioanalytical atorvastatin concentration results did not pass incurred sample reanalysis testing. Therefore, pharmacokinetic analysis of atorvastatin will not be performed.

The non-invasive fibrosis scores were not specified in the protocol. However, the fibrosis score components are from protocol-defined data points, and thus, the addition of the scores does not change how the data was collected, nor how the data points are defined.

Intentionally Left Blank

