14.2.3.1.2	EE	Summary of VLDL Cholesterol Concentration – CV Units
14.2.3.1.3	EE	Summary of VLDL Cholesterol Particle Size and Particle Concentration
14.2.3.2.1	ITT	Summary of VLDL Cholesterol Concentration – SI Units (MMRM)
14.2.3.2.2	ITT	Summary of VLDL Cholesterol Concentration – CV Units (MMRM)
14.2.3.2.3		Summary of VLDL Cholesterol Particle Size and Particle Concentration (MMRM)
14.2.4.1	EE	Summary of Total Cholesterol and Triglyceride Concentrations – SI Units
14.2.4.2	EE	Summary of Total Cholesterol and Triglyceride Concentrations – CV Units
14.2.5	EE	Summary of ApoA1, ApoB, ApoE, ApoCII, ApoCIII and Lp(a) Concentrations
14.2.6	EE	Summary of Reverse Cholesterol Metabolism
14.2.7	EE	Summary of Liver Biochemistry and Markers of Liver Function
14.2.8	EE	Summary of Liver Inflammation, Hepatic Apoptosis, and Fibrosis
14.2.9.1	EE	Summary of Glycemic Control
14.2.9.2	EE	Summary of Glycemic Control by Diabetes Status
14.2.10	EE	Summary of Liver Stiffness Measurements via Transient Elastography
14.2.11	EE	Summary of Liver Fibrosis Improvement via Transient Elastography
14.2.12.1	EE	Summary of Correlation Between Liver Stiffness via Transient Elastography and Liver Biopsy NASH CRN Criteria
14.2.12.2	EE	Summary of Correlation Between Liver Stiffness via Transient Liver Elastography and Liver Biopsy Modified Ishak Scoring Criteria
14.2.13.1	EE	Summary of FIB-4 Score
14.2.13.2	EE	Summary of APRI Score
14.2.13.3	EE	Summary of NFS Score
14.2.13.4	EE	BARD Score Shift from Baseline
14.2.14.1	EE	Summary of Anthropometric Measures and Blood Pressure
14.2.14.2	EE	Summary of Anthropometric Measures and Blood Pressure by Diabetes Status
14.2.14.3	EE	Summary of Blood Pressure by Antihypertensive Use
14.2.15.1	EE	Summary of Cardiovascular Risk Scores
14.2.15.2.1	EE	Summary of Cardiovascular Markers of Risk – SI Units
14.2.15.2.2	EE	Summary of Cardiovascular Markers of Risk – CV Units
14.2.16.1	PK	Summary of Plasma Concentrations for OCA, Glyco-OCA, Tauro-OCA, and Total OCA by Treatment and Visit
14.2.16.2	PK	Summary of PK Parameters for OCA, Glyco-OCA, Tauro-OCA, and Total OCA by Treatment and Visit

Table Number	Population	Table Title
14.2.17.1	APK	Summary of Week 16 Plasma Concentrations for Atorvastatin, 2OH-Atorvastatin, and 4OH-Atorvastatin by Treatment
14.2.17.2	APK	Summary of Week 16 PK Parameters for Atorvastatin, 2OH-Atorvastatin, and 4OH-Atorvastatin by Treatment
14.2.18.1	ITT	Summary of Total Bile Acids and Total Endogenous Bile Acids

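### Percentage change from Baseline is planned for the NAFLD fibrosis score (NFS), which can be negative or zero, so its sign reverses for negative Baselines and the group comparison loses direction and size

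*SAP*

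**What the plan says.** Section 3.3.3 introduces one set of endpoints with "For noninvasive scores of liver fibrosis NFS, FIB-4, and APRI" and lists observed values, change and percentage change from Baseline at every double-blind visit after Baseline. Section 9.3.5 keeps the three scores together: "Noninvasive scores of liver fibrosis including FIB-4, APRI, and NFS will be summarized with descriptive statistics at Baseline and each DB post-Baseline visit". It continues: "In addition, change and percentage change will be summarized and analyzed using the Wilcoxon Rank Sum Test to compare treatment groups". Hodges-Lehmann median differences with 95% confidence intervals follow. Percentage change in NFS is therefore a planned between-group comparison and not only a descriptive column.

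Two other sections supply the arithmetic. Section 6.3.5 defines percentage change as 100 times the difference between the post-Baseline and Baseline values, divided by the Baseline value as it stands, sign included. Section 6.3.7 defines NFS as a sum of weighted terms that starts at -1.675 and subtracts multiples of platelets and albumin.

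The SAP neither exempts NFS from percentage change nor says what to do when the Baseline is zero or negative. Appendix A lists the output as Table 14.2.13.3, "Summary of NFS Score".

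**The concern.** Percentage change needs a variable with a true zero and a positive Baseline. FIB-4 and APRI qualify, being products and ratios of positive quantities. NFS does not, because its zero is only the point where the weighted terms cancel.

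With a signed denominator, a subject with a negative Baseline whose score rises gets a negative percentage change. A subject with a positive Baseline and the same rise gets a positive one. Close to zero the value grows without limit, and at zero it is undefined.

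Ranking does not repair this. The Wilcoxon test and the Hodges-Lehmann estimate use the signed percentages, so a rise from a negative Baseline is ranked beside a fall from a positive one. Table 14.2.13.3 could then show NFS rising on the absolute scale and falling on the percentage scale for the same subjects, with nothing in the SAP to say which to believe.

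**Working it through.** The SAP states no figure for NFS, so there is none to reproduce. The check uses its own two formulas.

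**Formulas**

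- Section 6.3.7: NFS = -1.675 + 0.037 × age + 0.094 × BMI + 1.13 × (impaired fasting glucose or diabetes) + 0.99 × AST/ALT - 0.013 × platelets - 0.66 × albumin.
- Section 6.3.5: percentage change = 100 × (post - Baseline) / Baseline.

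**Both signs occur.** Assumed but ordinary inputs:

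| Age | BMI | Diabetes | AST/ALT | Platelets | Albumin | NFS |
|---|---|---|---|---|---|---|
| 50 | 33 | no | 0.7 | 240 | 4.3 | -1.99 |
| 55 | 34 | yes | 0.8 | 213 | 4.3 | -0.13 |
| 60 | 36 | yes | 1.0 | 180 | 4.0 | +1.07 |

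**One subject.** Take age 55, BMI 34, diabetes, AST/ALT 0.80 and albumin 4.3.

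- Terms other than platelets: -1.675 + 2.035 + 3.196 + 1.13 + 0.792 - 2.838 = 2.640.
- Platelets 230: 2.640 - 2.990 = -0.350.
- Platelets 215: 2.640 - 2.795 = -0.155.
- The rise is 0.195, reported as 100 × 0.195 / (-0.350) = -56%.

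The same rise of 0.195 on either side of zero:

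- Baseline platelets 203, NFS 2.640 - 2.639 = 0.001: +19,500%.
- Baseline platelets 204, NFS 2.640 - 2.652 = -0.012: -1,625%.

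One platelet unit at Baseline changes the sign of the result. Away from zero the reversal is just as plain: a rise of 0.3 is -20% from a Baseline of -1.5 and +20% from +1.5.

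**Group comparison.** The simulation used two arms of 20 (the group size in Section 5). The assumed between-group difference was +0.3 with a change SD of 0.3. The Baseline distribution is also assumed, with four profiles of means for age / BMI / diabetes / AST:ALT / platelets / albumin:

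- A: 48 / 33 / 40% / 0.70 / 250 / 4.4
- B: 52 / 34 / 50% / 0.78 / 230 / 4.35
- C: 56 / 35 / 60% / 0.85 / 210 / 4.3
- D: 60 / 36 / 70% / 0.95 / 190 / 4.2

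The SDs were 11, 5.5, 0.25, 65 and 0.35 for the continuous inputs in that order, each scaled by 0.6, 1.0 and 1.4. Rejection rates come from 20,000 runs and sign comparisons from 4,000. The three figures in each cell are for the three spreads.

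| Profile | Negative Baselines | Wilcoxon rejects, percentage change | Hodges-Lehmann estimates of opposite sign |
|---|---|---|---|
| A | 98 / 92 / 86% | 73 / 54 / 38% | 99.6 / 98.4 / 95.5% |
| B | 89 / 80 / 74% | 43 / 26 / 18% | 96.3 / 90.9 / 83.7% |
| C | 64 / 61 / 59% | 9 / 7 / 6% | 70.7 / 66.8 / 62.2% |
| D | 30 / 36 / 40% | 13 / 9 / 7% | 20.0 / 28.1 / 33.9% |

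On absolute change the test rejects in 84.5% to 85.3% throughout. With no treatment effect, the percentage-change test rejects in 4.8% to 5.2%.

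**Different assumptions, same pattern.** This second simulation used a true shift of +0.4, SD 0.4, 20 per arm, normal Baselines and 3,000 runs. Absolute change gave an estimate of about +0.40 and power of 84% to 86% in every case. Percentage change gave:

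| Baseline mean (SD) | Negative Baselines | Typical estimate | Wrong sign | Power |
|---|---|---|---|---|
| -1.5 (1.3) | 88% | -20% | 96% | 40% |
| -0.7 (1.5) | 68% | -12% | 77% | 11% |
| 0 (1.5) | 50% | -0.7% | 52% | 5% |
| +1.0 (1.0) | 16% | +27% | 6% | 35% |

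**The case against.** The strongest counter-argument concerns importance. Section 12 says of these scores: "The non-invasive fibrosis scores were not specified in the protocol". They are exploratory additions, and Section 6.2.8 says: "Therefore, CIs and p-values will be interpreted as purely descriptive". No primary or secondary endpoint, sample size or safety rule depends on NFS. Absolute change is planned in the same sentence with the same test and estimator, so nothing needed for interpretation is lost. With no formal hypothesis here, lost power carries little weight, and false positives are not inflated. All of this stands and limits the impact.

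Second, the magnitudes rest on assumptions. The SAP gives no NFS Baseline distribution or expected effect, and a share of negative Baselines anywhere from 30% to 98% does not say how far this trial would be affected. That is fair for the size but not for the fault, which follows from the SAP's formulas for any mix that includes negative Baselines.

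Third, the huge percentages need Baselines very near zero. Under the assumed profiles only about 1% to 4% of subjects lie within 0.05 of it, and an exact zero is very unlikely. Rank methods also bound the influence of extreme values. This stands too: the sign reversal is the main fault, and extreme values mostly spoil means and SDs.

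Fourth, if nearly all Baselines were negative, the reversal would be almost uniform and a careful reader could undo it. That is true of profile A with the narrow spread, but the SAP gives no such warning, and with mixed signs nothing can be undone.

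The general provision in Section 6.2 for switching to non-parametric methods does not help, because the planned test is already non-parametric.

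**Conclusion.** The concern holds. Carried out exactly as written, the plan gives percentage changes in NFS that are reversed for negative Baselines and unstable near zero. The Wilcoxon comparison and Hodges-Lehmann difference then mix correctly signed and reversed values. Under the assumed Baselines and a difference of +0.3 (SD 0.3, 20 per arm), the percentage-scale estimate contradicts the absolute-scale one in 20% to 99.6% of trials, and rejection falls from about 85% to between 6% and 73%. These ranges depend on the assumed Baseline mix and effect; the sign reversal does not.

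The fault is confined to percentage change in NFS. Absolute change in NFS, both scales for FIB-4 and APRI, and the primary LDL analyses are unaffected. The consequence is a potentially contradictory exploratory result, and the correction should be made because it costs almost nothing.

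**What to change.** In Section 3.3.3, separate NFS from FIB-4 and APRI and list only observed values and change from Baseline for it. In Section 9.3.5, limit percentage change, with its Wilcoxon test and Hodges-Lehmann estimate, to FIB-4 and APRI, and state that NFS is analysed as absolute change only. Omit any percentage-change columns from Table 14.2.13.3. The appendix gives only that table's title, so the columns are inferred from the two sections.

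The cost is wording in two sections and at most one set of output columns removed. Data collection and sample size are not affected.

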### **9.3.6. Anthropometric Measures and Blood Pressure**

Anthropometric measures (ie, body weight, waist and hip circumference measurements, BMI, and waist-to-hip ratio calculations) and blood pressure will be summarized using arithmetic summary statistics as described in [Section 6.2.1](#) at Baseline and at each DB post-Baseline visit. Change and percentage change from baseline will also be summarized in the same manner. Re-tests or unscheduled visit results after the first OCA dose administration time will not be summarized but will be included in the data listings.

Treatment groups will be compared using an ANCOVA model with change from Baseline as the dependent variable, including treatment group, and randomization stratification factors as fixed effects and baseline as a covariate. The same analysis will be carried out using percentage change from Baseline as the dependent variable. Estimates of LS means, SEs, and 95% CIs will be presented by treatment group. Estimates of the mean difference between each active treatment group and placebo group, the SE of the difference, and 95% CI of the difference will be presented.

Subgroup analyses will also be presented by diabetes status, excluding the randomization stratification factors from the ANCOVA model. Subgroup analyses of blood pressure will also be presented by use of antihypertensive medications.

### **9.3.7. Cardiovascular Risk Scores**

Cardiovascular risk scores including FRS and Reynolds scores will be calculated at the time of data analysis using the formulas in [Section 6.3.6](#). These scores will be summarized by treatment group and sex using arithmetic summary statistics as described in Section 6.2.1 at Baseline and at each DB post-Baseline visit. The change and percentage change from Baseline will also be summarized.

### **9.3.8. Cardiovascular Markers of Risk**

Cardiovascular markers of risk including adiponectin, PAI-1, and BNP will be summarized by treatment using arithmetic summary statistics as described in [Section 6.2.1](#) at Baseline and at each DB post-Baseline visit. The change and percentage change from Baseline will also be summarized.

While the protocol states PAI-1 and BNP will be stored for future analysis, it was later determined the samples would not maintain stability for future analysis, and thus were assayed for analysis.

## **10. EXPLORATORY PHARMACOKINETIC AND PHARMACODYNAMIC ANALYSIS**

Total OCA will be calculated as the micromolar concentration sum of unconjugated OCA, glyco-OCA, and tauro-OCA. Concentrations will be converted from ng/mL units to micromolar units as follows: concentration ( $\mu\text{M}$ ) = concentration (ng/mL) / molecular weight (MW). The MW weights for OCA are as follows: unconjugated OCA = 420.6 g/mol, glyco-OCA = 477.7 g/mol, and tauro-OCA = 527.8 g/mol. Total OCA in micromolar units can be converted to mass equivalents of OCA as follows: concentration (ng/mL) = concentration ( $\mu\text{M}$ ) \* 420.6. The PK Population will be used in the analyses of OCA PK (Day 1 and Week 16).

Further population PK/PD analyses may be conducted utilizing a separate appropriate plan to describe analysis methods. The methods and results would be included in a separate report.

### **10.1. Pharmacokinetic Measures**

At selected investigational sites, subjects will have the option to provide blood samples for measurement of OCA concentrations. On Day 1 and Week 16, PK samples will be collected within 30 minutes prior to dosing (predose) and at 0.5, 0.75, 1, 1.5, 2, 2.5, 3, 4, 5, and 6 hours postdose. Subjects should not drink additional water for 1 hour after taking the dose of investigational product and will remain fasted until the 1-hour sample is collected.

### **10.2. Pharmacokinetic Data Handling**

#### **10.2.1. Missing Values**

The lack of concentration values or dosing information due to failure to collect the sample or dosing information, a lost or compromised sample or due to the subject's early termination from the study may be termed "missing" in the dataset. If a missing value occurs for the time point prior to the first study drug administration, the value is set to zero. Otherwise, no imputation of missing values will be performed.

#### **10.2.2. Results Below Limit of Quantification (BLQ)**

For the purposes of PK parameter estimation, the following rules for BLQ results will be followed:

- BLQ values that occur prior to the first quantifiable concentration will be set to zero

- BLQ values occurring between two quantifiable values will be set to the lower limit of quantification (LLOQ) divided by 2
- BLQ values occurring after the last quantifiable value will be set to missing

#### **10.2.3. PK Sampling Times**

Actual (rather than nominal) PK sample collection times will be used for the purposes of PK parameter estimation.

#### **10.2.4. Decision Paradigm for Reprocessing Samples**

The PK sample reprocessing paradigm will be detailed in the bioanalytical report. Intercept Clinical Pharmacology may issue a request for sample reprocessing if an observed concentration represents an unexplained, significant deviation from temporal consistency with the prior and following samples in the affected subject's concentration-time profile. Reprocessing will only take place if sufficient sample volume exists.

#### **10.2.5. Anomalous Concentration Handling**

Anomalous concentration values are those that, after verification of bioanalytical validity, are grossly inconsistent with the known or expected pharmacokinetics behavior of the drug. The clinical pharmacologist will use his/her discretion regarding the handling of this data. The rationale will be documented within the study report. Any such anomalous concentrations data will be documented in the clinical study report.

#### **10.2.6. Representation of Mean Concentrations**

All values reported as below the limit of quantitation (BLQ) will be replaced with zero for mean representation in figures. In the tables presenting summary statistics of concentration-time series, the total number of values (n) and the number of values that are BLQ will be presented to allow appropriate interpretation of the data.

If missing observations at a nominal time point exceed 50% of the observations collected at that nominal time point, summary statistics for the time point will not be calculated.

If the mean concentration value is less than the LLOQ, then the mean concentration value will be set to BLQ in tables and missing in graphics.

The central tendency and dispersion of OCA (and its conjugates and metabolite) concentration-time data will be graphically represented as the Mean (optional +/- SD) by nominal time point in linear scale and semi-log scale by visit. Median by nominal time point representations may also be presented if deemed appropriate.

PK samples that have a significant time deviation from the planned sampling time will be considered as "missing" for the calculation of concentration summary statistics at that nominal time point. Acceptable PK sampling time windows are defined in the table below:

Nominal PK Sampling Time	Acceptable Sampling Window
--------------------------	----------------------------

Pre-dose	Within 30 minutes prior to dosing
0.5 h, 0.75 h	+/- 5 minutes relative to nominal
1 h	+/- 10 minutes relative to nominal
1.5h, 2 h, 2.5 h, 3 h, 4 h, 5 h, 6 h	+/- 15 minutes relative to nominal

Only samples from subjects with confirmed fasting of  $\geq 8$  hours prior to dosing will be included in summaries. Individual subject plasma concentrations, including derived concentrations for total OCA, will be listed by analyte and formulation and summarized with descriptive statistics on Day 1 and on Week 16 by treatment group as defined in [Section 6.2.1](#) and [Section 6.2.7](#), including geometric coefficient of variation (CV%).

## 10.3. Pharmacokinetic Analysis

### 10.3.1. Pharmacokinetic Methods

PK parameters for OCA and its conjugates, and total OCA will be determined using standard non-compartmental methods. Pharmacokinetics will be summarized in tabular and graphical forms. The primary PK parameter estimations in this study are:

For both Day 1 and Week 16:

- $C_{\max}$  (ng/mL): Maximum observed concentration obtained by inspection of the data. If all observations are below the limit of quantification (BLQ),  $C_{\max}$  will be reported as zero.
- $t_{\max}$  (h): First time at which  $C_{\max}$  is observed and is obtained by inspection of the data. If all observations are BLQ,  $t_{\max}$  will be reported as not determined (ND).
- $AUC_{0-6}$  (hr\*ng/mL): Area under the concentration versus time curve from zero time until the last sampling time (hour 6).
  - The linear interpolation rule should be used for estimation of area under the concentration-time curve (AUC).
  - Where the clinical pharmacologist identifies that another method is more appropriate, the reason for this decision should be documented.
  - A minimum of 4 measurable values are required for AUC calculation
  - For last sampling times  $>6$  hours,  $AUC_{0-6}$  will be interpolated. For last sampling times from 5.75 to 6 hours,  $AUC_{\text{last}}$  will be reported for  $AUC_{0-6}$ . For last sampling times  $<5.75$  hours,  $AUC_{0-6}$  will not be reported.
- Dose-normalized versions of  $C_{\max}$  and  $AUC_{0-6}$  will be calculated for Day 1 and Week 16.

- Metabolite ratios based on  $C_{max}$  ( $MRC_{max}$ ) and  $AUC_{0-6}$  ( $MRAUC_{0-6}$ ) will be calculated:

$MR\ C_{max} = (C_{max}\ conjugate\ or\ metabolite\ / C_{max}\ parent) \times (molecular\ weight\ parent\ / molecular\ weight\ conjugate\ or\ metabolite)$

$MR\ AUC_{0-6} = (AUC_{0-6}\ conjugate\ or\ metabolite\ / AUC_{0-6}\ parent) \times (molecular\ weight\ parent\ / molecular\ weight\ conjugate\ or\ metabolite)$

Accumulation [only for OCA and its conjugates]:

- Steady-state accumulation ratios based on  $C_{max}$  ( $R_{ac}\ C_{max}$ ) and  $AUC_{0-6}$  ( $R_{ac}\ AUC_{0-6}$ ) will be calculated:

$R_{ac}\ C_{max} = \text{Week 16 } C_{max} / \text{Day 1 } C_{max}$

$R_{ac}\ AUC_{0-6} = \text{Week 16 } AUC_{0-6} / \text{Day 1 } AUC_{0-6}$

Additional parameters may be calculated in order to further characterize PK, if deemed necessary.

